10.1.2.2 Adverse Events

Adverse Event Definition

An AE is defined as any untoward medical occurrence in a clinical study subject administered a medicinal product which does not necessarily have a causal relationship with this treatment. An AE can therefore be any unfavorable and unintended sign (including an abnormal laboratory finding), symptom, or disease temporally associated with the use of a medicinal (investigational) product, whether or not it is related to the medicinal (investigational) product. This includes an exacerbation of pre-existing conditions or events, intercurrent illnesses, drug interaction or the significant worsening of the indication under investigation that is not recorded elsewhere in the eCRF under specific efficacy assessments. Anticipated fluctuations of pre-existing conditions, including the disease under study that do not represent a clinically significant exacerbation or worsening need not be considered AEs.

It is the responsibility of the investigator to document all AEs that occur during the study. AEs will be elicited by asking the subject a nonleading question, for example, "Have you experienced any new or changed symptoms since we last asked/since your last visit?". AEs should be reported on the appropriate page of the eCRF.

CONFIDENTIAL

Assessment of Severity

Each AE will be assigned a category by the investigator as follows:

Mild: An AE that is easily tolerated by the subject, causes minimal discomfort and does not interfere with everyday activities.

Moderate: An AE that is sufficiently discomforting to interfere with normal everyday activities; intervention may be needed.

Severe: An AE that prevents normal everyday activities; treatment or other intervention usually needed.

If there is a change in severity of an AE, it must be recorded as a separate event.

Assessment of Causality

Every effort will be made by the investigator to assess the relationship of the AE, if any, to the study drug. Causality should be assessed using the categories presented in the following table:

Unrelated: Clinical event with an incompatible time relationship to study drug administration, and that could be explained by underlying disease or other drugs or chemicals or is incontrovertibly not related to the study drug.

Unlikely: Clinical event whose time relationship to study drug administration makes a causal connection improbable, but that could plausibly be explained by underlying disease or other drugs or chemicals.

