For subjects receiving escitalopram 20 mg/day, the doses given during the double-blind down taper period will be as follows:

Week 9: Subjects will receive 10 mg/day.

AbbVie Escitalopram

SAP SCT-MD-60 Allergan

Page 9 of 53

Subjects randomized to the placebo arm will receive matching placebo during the double-blind acute treatment period. Subjects evaluated at the end of Week 2 and Week 4 and tolerating 10 mg/day matching placebo may be indicated for dose escalation by the investigator but in a blinded fashion will continue to receive matching placebo. Subjects receiving placebo will follow a similar down tapering schedule at the end of the double-blind acute treatment period.

A follow-up telephone contact will take place 1 week after the end of the double-blind down taper period.

[figure not shown]
A blinded interim analysis will be conducted when 75% of randomized subjects have either completed or discontinued the study in order to check the assumptions in the sample size calculation. Based on this, the sample size may be increased to ensure an adequate power. However, due to the difficulties in recruiting pediatric subjects with GAD, the number of subjects in each treatment arm will be capped at 160.

The study design is shown in Figure 1.

Page 10 of 53

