10.1 ADVERSE EVENTS

Adverse events will be coded by SOC and PT using the MedDRA version 22.0 or newer.

An AE (classified by PT) that occurs during the double-blind acute treatment period, during the down-taper period, or within 30 days after the date of the last dose of double-blind investigational product will be considered a treatment-emergent adverse event (TEAE) if it was not present before the date of the first dose of double-blind investigational product, or was present before the date of the first dose of double-blind investigational product and increased in severity during the double-blind acute treatment period or during the down-taper period, respectively.

If more than 1 AE was reported before the date of the first dose of double-blind investigational product and coded to the same preferred term, the AE with the greatest severity will be used as the benchmark for comparison with the AEs occurring during the double-blind acute treatment period or during the down-taper period that were also coded to that preferred term. An AE that occurs more than 30 days after the date of the last dose of double-blind investigational product in the study will not be counted as a TEAE but will be included in the listings.

Page 31 of 53

An AE occurring during the down-taper period or safety follow-up period will be considered a newly emergent AE (NEAE) if it is not present before the start of the down-taper period or was present before the start of the down-taper period but increased in severity during the down-taper period. All NEAEs will be summarized by SOC, PT, and treatment group.

The number and percentage of subjects in each treatment group reporting TEAEs during the double-blind acute treatment period will be tabulated by SOC and PT; by SOC, PT, and severity; and by SOC, PT, and causal relationship to the investigational product. If more than one AE is coded to the same PT for the same subject, the subject will be counted only once for that PT using the most severe and most related occurrence for the summarization by severity and by causal relationship to the investigational product, respectively. Study-treatment-related TEAEs are defined as TEAEs with relationship to treatment categorized as Possible, Probable, Very, Like/Certain or missing.

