The distribution of TEAEs by severity and causal relationship to the investigational product will be summarized by treatment group. The incidence of common ($\geq 2\%$ of subjects in any treatment group) TEAEs during the double-blind acute treatment period will be summarized by PT and treatment group.

A serious adverse event (SAE) that occurred between the date of the first dose of double-blind investigational product and 30 days after the date of the last dose of double-blind investigational product in the study, inclusive, will be considered an on-therapy SAE. The incidence of SAEs and AEs leading to premature discontinuation of the study will also be summarized by study period (separately for double-blind acute treatment period and double-blind down taper period), SOC, PT, and treatment group.

The above summaries will be sorted by decreasing frequency of SOC and by the decreasing frequency of PT within SOC for the escitalopram treatment group. If incidence for more than 1 term is identical, they will then be sorted alphabetically. In addition, the above summaries will be presented as all AEs, AEs that are associated with the COVID-19 pandemic (as determined by the investigator), and AEs that are not associated with the COVID-19 pandemic. AEs associated with the COVID-19 pandemic will be listed separately.

Listings will be presented for subjects with SAEs, subjects with AEs leading to premature discontinuation, and subjects who died for the Screened Population. All subjects with SAEs, including those reported during the screening period or more than 30 days after the date of the last dose of the double-blind investigational product, and subjects discontinuing due to AEs before the start of double-blind investigational product will be included in these listings

Page 32 of 53

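### SAP 10.1 counts new adverse events as newly emergent through the safety follow-up, but worsening of existing events only to the end of the taper

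*SAP*

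**What the plan says.** **NEAE rule (SAP 10.1).** The opening of the definition covers two periods: "An AE occurring during the down-taper period or safety follow-up period will be considered a newly emergent AE (NEAE"). It then has two limbs. One admits events absent before the taper. The other admits events "present before the start of the down-taper period but increased in severity during the down-taper period". The second limb does not mention the follow-up.

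**TEAE rule (SAP 10.1).** The outer window includes events "within 30 days after the date of the last dose of double-blind investigational product will be considered a treatment-emergent adverse event (TEAE"). An event that predates the first dose must have "increased in severity during the double-blind acute treatment period or during the down-taper period, respectively". The sentence that sets the worst pre-dose grade as the benchmark likewise compares it only with events in the acute and taper periods.

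**Tables (SAP 10.1).** The main TEAE tables count subjects "reporting TEAEs during the double-blind acute treatment period will be tabulated by SOC and PT", with versions by severity and causality. The common-TEAE table is also limited to the acute period. One summary names no period: "The distribution of TEAEs by severity and causal relationship to the investigational product will be summarized by treatment group". Tables of serious AEs (SAEs) and of discontinuations due to AEs are split into acute and taper periods only.

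**Protocol.** Section 11.6.1.1 confines both NEAE limbs to the taper and puts no period limit on worsening of a pre-dose event for TEAE purposes. Section 10.1.2.2 collects AEs to 30 days after the last dose and requires: "If there is a change in severity of an AE, it must be recorded as a separate event".

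**Taper dosing (Protocol 8.4.1, SAP 3.0).** Subjects who finish on 10 mg/day take placebo in Week 9. For those who finish on 20 mg/day: "Week 9: Subjects will receive 10 mg/day".

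**The concern.** The two NEAE limbs end at different times, and the later part of the window is open only to new events. That part matters because the final step to zero drug, for anyone tapered from 20 mg/day, comes after the last taper dose. Protocol 8.3.5 asks sites to watch for anxiety, irritability, agitation, insomnia and headache, among other symptoms, when treatment stops. In a trial of generalized anxiety disorder, such terms may well be on record before the taper, so a discontinuation effect could show as worsening rather than as a new event.

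Placebo subjects have no active drug to come off. A rule that overlooks worsening in this interval is therefore more likely to undercount on escitalopram than on placebo. Safety is part of the primary objective, and the NEAE table is where a reader would look for discontinuation effects.

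**Working it through.** No figure in the plan needs reproducing. The check sorts events by when they began, takes a non-serious worsening after the last taper dose, and applies the SAP 10.1 definitions with matching by PT.

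1. **Present before first dose, worsens only after the taper.** Not an NEAE: it was present before the taper and the increase fell outside it. Not a TEAE: the increase fell outside the acute and taper periods. It enters neither set of tables.
2. **Began in the acute period, worsens after the taper.** Not an NEAE, for the same reason. The subject is already in the acute TEAE table at the earlier grade. The worsened record is itself a TEAE, because the event was absent before first dose and falls within 30 days of the last dose. It lies outside the acute-only tables but could enter the severity distribution that names no period. The worsening is missing from the NEAE table.
3. **Began in the taper, worsens later.** Already an NEAE, because it was absent before the taper.
4. **New in follow-up.** NEAE through the onset limb.

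The gap is therefore confined to cases 1 and 2. Because the TEAE tables by SOC and PT cover the acute period only, no other general table by SOC and PT picks up the worsening in those cases.

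**When drug leaves.** Protocol 6 gives a terminal half-life of about 27 to 32 hours. The fraction left 7 days (168 h) after the last active dose is 0.5^(168/t½):
- t½ = 27 h: 0.5^(6.22) = 1.3%
- t½ = 32 h: 0.5^(5.25) = 2.6%

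A subject finishing on 10 mg/day takes the last active dose at about the end of Week 8, so almost all of the decline falls in Week 9, where worsening counts. A subject finishing on 20 mg/day is still taking 10 mg/day in Week 9. The decline from that level to zero begins after the last taper dose, where worsening does not count.

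**SAP against protocol.** For TEAEs, the SAP adds a period limit to worsening that Protocol 11.6.1.1 does not have. For NEAEs, it extends onset into follow-up, beyond the protocol, and leaves worsening at the taper. SAP 17.0 lists one departure from the protocol, on weight and height z-scores, and declares no others.

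**The case against.** The strongest reply is that little is truly lost. New symptoms after the last dose are counted, and so are events that began in the taper. Subjects with acute-onset events stay in the acute TEAE table. A serious worsening within 30 days meets the on-therapy SAE definition, and all SAEs are listed. All of this stands. A reader might infer that events worsening after the last dose reach no incidence table at all. The documents do not support that: only non-serious events already present before first dose miss both definitions.

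Second, the exclusion depends on matching by PT. The SAP states that matching for TEAEs but does not repeat it for NEAEs. Since a change in grade is recorded as a separate event, record-level programming could let the worsened record in through the onset limb. This is a fair limit on the claim. It also shows that the text leaves the result to the programmer.

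Third, the NEAE worsening limb matches the protocol, and pulling onset back to the taper would also make the limbs agree. That is true. But it would remove new follow-up events from the only general table by SOC and PT that shows them.

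Fourth, rewording the TEAE limb would not alter the acute-only tables. This stands too: the effect there is on the summary that names no period and on agreement with the protocol.

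**Conclusion.** The point holds as a mismatch in SAP 10.1. Followed as written, with matching by PT, the plan does not count worsening after the last taper dose as newly emergent when the event was present before the taper. For non-serious events that predate the first dose, it does not count as treatment-emergent either, an undeclared narrowing of the protocol rule. What is lost is the post-taper worsening from the NEAE table, not the subject from every table.

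No count can be attached. The documents give neither the share of subjects expected to finish on 20 mg/day nor a rate of worsening after stopping. The half-life arithmetic shows when exposure ends, not how many events are missed. The direction is clearer than the size: any undercount is more likely on escitalopram.

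This rests on three assumptions: PT-level matching for NEAEs; a taper period that ends with the last taper dose (SAP Table 16.1–2 does not tie its end to a day, so an end at the Week 9 visit could capture a little more); and the protocol's half-life applying to these subjects. No efficacy result is affected.

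**What to change.** In SAP 10.1, before unblinding:

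- In the NEAE definition, extend the worsening limb to read *increased in severity during the down-taper period or safety follow-up period*.
- Define the safety follow-up period, which the SAP leaves undefined, as ending 30 days after the last dose of double-blind investigational product. This is the limit already used for TEAEs and for AE collection.
- State that NEAE matching is by PT.
- Give the TEAE worsening limb and the severity-benchmark sentence the same 30-day window, in line with Protocol 11.6.1.1.
- List in SAP 17.0 the extension of NEAEs into follow-up, which goes beyond the protocol.

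The cost is a few phrases and the matching programming. The data are already collected and worsened events already recorded separately, so no new visits or subjects are needed. The downside is that NEAE counts may be slightly higher.

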10.2 CLINICAL LABORATORY PARAMETERS

Descriptive statistics for clinical laboratory values (in SI units) and changes from the baseline values at each assessment time point (including the end of the double-blind acute treatment period) will be presented by treatment group for the following laboratory parameters:

Hematology: Hemoglobin, hematocrit, white blood cell count (total and

differential), red blood cell count, platelet count, mean cell volume, mean cell hemoglobin (MCH), and MCH concentration.

Chemistry: Creatinine, urea (or blood urea nitrogen), aspartate transferase,

alanine transferase, gamma glutamyltransferase, alkaline phosphatase, lactate dehydrogenase, total bilirubin, albumin, total protein, sodium, potassium, chloride, glucose, uric acid, calcium,

phosphorus, thyroid-stimulating hormone, T3, and T4.

Urinalysis: pH, glucose, ketones, blood, protein, and microscopy.

Clinical laboratory test values will be considered potentially clinically significant (PCS) if they meet either the lower-limit or higher-limit PCS criteria listed in Table 10.2–1. The number and percentage of subjects who have PCS post-baseline clinical laboratory values will be tabulated by treatment group. The percentages will be calculated relative to the number of subjects with available non-PCS baseline values and at least 1 postbaseline assessment. The numerator will be the total number of subjects with available non-PCS baseline values and at least 1 PCS post-baseline value. A supportive listing of subjects with PCS post-baseline values will be provided, including the subject identification (SID) number, study center number, and baseline and all post-baseline (including non-PCS) values.

In addition, a listing of all AEs that occurred in subjects who had PCS post-baseline clinical laboratory values will be provided.

Table 10.2–1. Criteria for Potentially Clinically Significant Laboratory Values

Parameter	SI Unit	Lower Limit	Higher Limit
HEMATOLOGY			
Basophils	%		> 6
Eosinophils	%		> 10
Hematocrit	1.0	< 0.9 × LLN	
Hemoglobin	g/L	< 0.9 × LLN	
Lymphocytes	%	< 10	> 60
Monocytes	%	_	> 20
Neutrophils	%	< 30	> 90
Platelet count	× 10 ⁹ /L	≤ 75	≥ 700

Page 33 of 53

White blood cell count	$\times 10^9/L$	≤ 2.5	≥ 15
CHEMISTRY			
Albumin	g/L	< 0.9 × LLN	> 1.1 × ULN
Alkaline phosphatase	U/L	_	\geq 3 × ULN
Alanine	U/L		\geq 3 × ULN
aminotransferase	U/L	_	≥ 3 ^ OLN
Aspartate	U/L		\geq 3 × ULN
aminotransferase			_
Bicarbonate	mmol/L	< 0.9 × LLN	> 1.1 × ULN
Blood urea nitrogen	mmol/L		> 1.2 × ULN
Calcium	mmol/L	< 0.9 × LLN	> 1.1 × ULN
Chloride	mmol/L	< 0.9 × LLN	> 1.1 × ULN
Cholesterol, total	mmol/L	_	> 200mg/dL
Creatinine	μmol/L	_	> 1.3 × ULN
Glucose	mmol/L	< 0.8 × LLN	> 1.4 × ULN
high-density		< 40 m ~/4I	
lipoprotein	mmol/L	< 40 mg/dL	_
Low-density lipoprotein	mmol/L	_	> 130 mg/dL
Magnesium	mmol/L	< 0.9 × LLN	> 1.1 × ULN
Phosphate	mmol/L	< 0.9 × LLN	> 1.1 × ULN
Potassium	mmol/L	< 1.0 × LLN	> 1.0 × ULN
Sodium	mmol/L	< 1.0 × LLN	> 1.0 × ULN
Total bilirubin	μmol/L	_	> 1.5 × ULN
Total protein	g/L	< 0.9 × LLN	> 1.1 × ULN
Triglyogrido	mmol/L		> 100 mg/dL (ages 7-10),
Triglyceride	IIIIIIOI/L		>130 mg/dL (ages 11-17)
URINALYSIS			
Protein	g/L		at least two +
Glucose	mmol/L	_	at least two +

LLN = lower limit of normal value provided by the laboratory; SI = Le Système International d'Unités (International System of Units); ULN = upper limit of normal value provided by the laboratory.

Shift tables from baseline to the end of double-blind acute treatment period for clinical laboratory parameters will be presented by treatment group for the following categories: low, normal, and high.

Potential Hy's Law criteria is defined by a postbaseline elevation of alanine aminotransferase (ALT) or aspartate aminotransferase (AST) \geq 3× ULN (ULN = upper limit of normal laboratory reference range), along with total bilirubin (TBL) \geq 2× ULN and a non-elevated alkaline phosphatase (ALP) < 2× ULN, all based on blood draws collected within a 24-hour period. The number and percentage of subjects who meet the following criteria of clinical interest during the double-blind acute treatment period will be tabulated by treatment group. A supportive list will also be provided.

• ALT: $\geq 3 \times$ ULN, $\geq 5 \times$ ULN, $\geq 10 \times$ ULN, $\geq 20 \times$ ULN

Page 34 of 53

- AST: $\geq 3 \times ULN$, $\geq 5 \times ULN$, $\geq 10 \times ULN$, $\geq 20 \times ULN$
- ALT or AST: $\geq 3 \times$ ULN, $\geq 5 \times$ ULN, $\geq 10 \times$ ULN, $\geq 20 \times$ ULN
- TBL: > 1.5 x ULN. 2 × ULN
- ALP: $< 2 \times ULN$
- Concurrent elevations:
 - ALT or AST \geq 3× ULN with TBL \geq 1.5× ULN;
 - ALT or AST \geq 3× ULN with TBL \geq 2× ULN;
 - ALT or AST \geq 3× ULN with TBL \geq 2× ULN and ALP < 2× ULN.

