10.1.2.2.6 Potential Hy's Law Cases

Criteria for potential Hy's law cases are as follows:

- Alanine aminotransferase (ALT) or aspartate aminotransferase (AST) $\geq 3 \times$ upper limit of normal (ULN) AND
- Total bilirubin $\geq 2 \times$ ULN AND
- Alkaline phosphatase $< 2 \times$ ULN

Study site personnel must report every subject who meets these criteria. Typically, all 3 analytes will be obtained from the same sample, but they may come from multiple samples taken within a 24-hour period. This requirement applies from the time the subject signs the ICF for the study until 30 days after receiving the last dose of study drug.

A laboratory alert for potential Hy's law cases will be in place, and the laboratory must notify investigators and the sponsor immediately when the above criteria have been met. A potential Hy's law case must be reported to the sponsor on an SAE form as soon as possible (within 24 hours of learning of the potential Hy's law case) to the SAE/pregnancy fax number, even if no AE has occurred. The eCRF for potential Hy's law cases must be completed within 7 calendar days. Every effort to determine the cause of the liver enzyme abnormalities must be made, and close monitoring should be initiated in conjunction with the Study Medical Monitor and in accordance with the FDA Guidance for Industry, Drug-Induced Liver Injury: Premarketing Clinical Evaluation, July 2009. The patient should return to the study site and be evaluated as soon as possible, preferably within 48 hours from the time the investigator becomes aware of the abnormal results. This evaluation should include laboratory tests, detailed history, and physical examination.

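### In SAP 10.2 the stand-alone liver criterion ALP < 2 × ULN counts subjects without an ALP elevation, and no planned count isolates ALP of 2 to < 3 × ULN

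*SAP*

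**What the plan says.** SAP 10.2 defines potential Hy's law cases as ALT or AST ≥ 3 × ULN with total bilirubin ≥ 2 × ULN and "a non-elevated alkaline phosphatase (ALP) < 2× ULN, all based on blood draws collected within a 24-hour period". It then calls for a table by treatment group of "subjects who meet the following criteria of clinical interest during the double-blind acute treatment period will be tabulated by treatment group", and adds: "A supportive list will also be provided".

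The list that follows has these parts:

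- ALT, AST, and ALT or AST, each at ≥ 3, 5, 10 and 20 × ULN.
- Total bilirubin, starting at > 1.5 × ULN.
- ALP < 2 × ULN, as a row of its own.
- Concurrent elevations, the last of which is the full Hy's law combination, including ALP < 2 × ULN.

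Three other parts of the plan bear on ALP. Table 10.2–1 sets the potentially clinically significant (PCS) limit at ≥ 3 × ULN. The laboratory shift tables "will be presented by treatment group for the following categories: low, normal, and high". SAP 10.0 and 10.2 together give ALP the usual descriptive statistics, including the maximum.

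Protocol 10.1.2.2.6 uses the same < 2 × ULN condition, joined by AND to the transaminase and bilirubin elevations. Protocol 11.6.1.4 does not ask for a stand-alone ALP row.

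**The concern.** A table of criteria of clinical interest should count subjects with a finding. The ALT, AST and bilirubin rows do so. The ALP row runs the other way, because it picks out subjects whose ALP the SAP itself describes as not elevated. Inside the Hy's law combination that condition does useful work by qualifying a transaminase and bilirubin rise. On its own it qualifies nothing.

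Two things follow for the reader of the study report. A row and a list that should draw attention to a few subjects would instead hold most of those tested. And the table would give no direct count of subjects with ALP at or above 2 × ULN, which helps in interpreting an isolated ALT or bilirubin rise.

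**Working it through.** The plan states no figure for this table, so there is none to reproduce. The check has two parts.

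**1. Which planned count captures a given ALP value?** Inputs: the stand-alone row (< 2 × ULN) and the shift category *high* (taken as above ULN), both from SAP 10.2; the PCS limit (≥ 3 × ULN) from SAP Table 10.2–1; and, for comparison, a row at ≥ 2 × ULN.

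| ALP (× ULN) | Row < 2 | PCS ≥ 3 | Shift *high* | Row ≥ 2 (proposed) |
|---|---|---|---|---|
| 0.8 | yes | no | no | no |
| 1.5 | yes | no | yes | no |
| 1.99 | yes | no | yes | no |
| 2.0 | no | no | yes | yes |
| 2.5 | no | no | yes | yes |
| 2.99 | no | no | yes | yes |
| 3.0 | no | yes | yes | yes |
| 4.0 | no | yes | yes | yes |

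Values from 2.0 to 2.99 × ULN meet neither ALP threshold. The only planned category they enter is *high*, where 2.5 × ULN cannot be told apart from 1.5 × ULN.

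**2. How large would the row be?** Let n be the number tested in an arm and q the proportion with ALP ≥ 2 × ULN. With one draw per subject:

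expected count in the row as written = n × (1 − q)

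expected count at ≥ 2 × ULN = n × q

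Take n = 128, the planned arm size in Protocol 8.3.1. This is for illustration; fewer may have a post-baseline sample, but the percentages do not depend on n. The documents give no ALP distribution for this age group, so q is assumed over a range.

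| Assumed q | Row as written: 128 × (1 − q) | Percent | Row at ≥ 2 × ULN: 128 × q |
|---|---|---|---|
| 0% | 128 | 100% | 0 |
| 1% | 126.7 | 99% | 1.3 |
| 2% | 125.4 | 98% | 2.6 |
| 5% | 121.6 | 95% | 6.4 |
| 10% | 115.2 | 90% | 12.8 |

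Across this range the row holds at least 90% of tested subjects. Inclusion criterion 13 (Protocol 8.3.2) admits out-of-range chemistry only if the investigator judges it not clinically relevant. That makes a large q less likely but does not fix its value.

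**The case against.** The strongest reply is that little information is lost. The maximum ALP in each arm appears in the descriptive statistics, and SAP 16.3 puts every assessment in the data listings. A reader might infer that an ALP between 2 and 3 × ULN would be invisible apart from the shift table; those provisions show otherwise.

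The missing count can also be approximated. Chemistry has one scheduled post-baseline draw, at Week 8 or early withdrawal (Protocol 9.2.5). Subjects assessed minus the ALP row is therefore roughly the number at ≥ 2 × ULN, and removing those at ≥ 3 × ULN leaves the 2 to < 3 band. Similarly, comparing the last two concurrent rows shows how many subjects with both elevations did not have ALP below 2 × ULN. This stands, within limits: the SAP gives no denominator for this table, a subject with repeat draws can meet < 2 × ULN despite a raised value, and the PCS count leaves out subjects who were PCS at baseline. The comparison of concurrent rows does not help with isolated ALT or bilirubin rises.

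A second reply is that the list walks through the components of Hy's law, so the ALP row merely displays the third one. That explains how the row may have arisen but does not justify it, because the component is already counted in the last concurrent criterion.

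Three further inferences are tempting and unsupported. True elevations cannot be called near zero, because q is unknown; at 10% about 13 per arm would be expected. Nor can the list be said to hold almost the whole Safety Population, because SAP 3.0 places the listing specifications in a separate document. Finally, the adjacent bilirubin line looks irregular, but probably because a symbol was lost in text extraction, so it is not treated as an error here.

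**Conclusion.** The row is wrong as written. It sits among elevation thresholds but selects subjects without an elevation, about 90% to 100% of those tested if 0% to 10% have ALP ≥ 2 × ULN. That range is an assumption. The absence of a planned threshold count for 2 to < 3 × ULN follows from the text alone.

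The effect is confined to one table row and any list built on it. A reader might infer that potential Hy's law cases would be miscounted. They would not: the combined criterion in SAP 10.2 matches Protocol 10.1.2.2.6, and the laboratory alert and 24-hour reporting of such cases do not depend on this table. No endpoint or test changes. This is a minor safety-reporting correction.

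**What to change.** Change the stand-alone row in SAP 10.2, and its supportive list, to ALP ≥ 2 × ULN. Keep < 2 × ULN only within the concurrent criterion. No document requires a cut-off at 2 × ULN for a row of its own, but it is the complement of the limit the SAP already uses for non-elevated ALP. Deleting the row would remove the oddity but leave the 2 to < 3 × ULN band without a count. Stating the table's denominator in the same edit would be useful.

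The cost is one symbol in the SAP and matching changes to the table and listing shells. No data collection or clinical procedure is affected.
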